### **11.2 Statistical Analysis**

The incidence of PTS, thrombotic recurrence, major bleeding and clinically relevant non-major bleeding will be reported as proportions. These outcomes will be compared at 3 and 6 months using Chi-square or Fisher's exact tests. A Cox-proportional hazards model will be utilized to calculate the risk of PTS and thrombosis recurrence. Chi-square or Fisher's exact tests will be used to determine if clot presentation or location predicts PTS or thrombotic recurrence. Agreement between the DASH and QuickDASH scales will be assessed using the intraclass correlation coefficient. To compare the discriminating ability of the DASH and QuickDASH on the level of PTS, receiver operating curves will be developed using the scale scores at 6 months as the test variable and dichotomized PTS assessment as the classifying variable. Levels of D-dimer, thrombin generation, and TFPI will be reported as means. Logistic regression will evaluate if D-dimer, thrombin generation or TFPI levels at 1 month or % change from baseline predict thrombotic recurrence. Where necessary, for parametric assumption, we will employ appropriate transformations with justifications. For example, the log of some of the biomarkers data may be used if the data range is >1000. Statistical

significance will be determined with  $p < 0.05$ . SAS version 9.13 and JMP 10 Statistical software will be employed for data analysis.

An interim analysis will be completed after 20 patients complete 6 months of follow-up. The interim analysis will allow assessment of thrombotic recurrence by the DSMC.

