
estimates will allow an appropriate comparison of duration of anticoagulation to be selected for a future randomized trial.

**Table 1:** Care of patients with CRT in practice vs. research protocol

	Typical Care Approach	Research protocol
Catheter removal	Not needed or malfunction	Not needed or malfunction
Anticoagulation Type	LMWH (enoxaparin or dalteparin)  Direct oral anticoagulant	Enoxaparin or direct oral anticoagulant
Duration of anticoagulation	1-3 months after catheter removal	1 month after catheter removal

A clinical scoring system or biomarker to predict recurrent catheter-related thrombosis in cancer patients do not exist. Currently patients are treated with anticoagulation for varying amounts of time based on local practice and extrapolation from clinical trials in lower extremity thrombosis. Development of biomarkers predictive of thrombosis would allow targeting of anticoagulation strategies in cancer patients at highest risk of thrombosis. The Ottawa score allows prediction of recurrent thrombosis in cancer patients and is based upon gender, history of thrombosis, cancer type and stage. The Khorana score integrates site of cancer, body mass index, and pre-chemotherapy platelet, leukocyte and hemoglobin levels to predict initial thrombosis. The Khorana score has not been evaluated as a predictor of thrombotic recurrence and will be assessed from clinical information at the time of CRT diagnosis. Validations of the Khorana score have also added biomarkers including D-dimer to expand the ability to detect high risk groups. Additionally, high levels of thrombin generation have been associated with increased risk of initial thrombosis in cancer patients. Elevated D-dimer and peak thrombin generation have been shown to be risk factors for recurrent thrombosis in non-cancer patients, but the association has not been evaluated in cancer patients. Tissue Factor Pathway Inhibitor (TFPI) functions to limit the activation of factor X by the tissue factor/Factor VIIa complex. TFPI has been shown to be a predictor of thrombosis with low levels of TFPI antigen associated with twice the risk of thrombosis. Platelet TFPI may also play a role in thrombotic risk as platelets accumulate at the site of injury. Platelet TFPI has not been assessed as a risk factor for thrombosis. Lastly, extracellular DNA released from neutrophils (NETs-neutrophil

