### **2.2 Clinical Objectives:**

- 3) To determine the incidence of post-thrombotic syndrome, thrombotic recurrence and bleeding in cancer patients with catheter-related thrombosis treated with 1 month of anticoagulation
  - a. Success of the study will be defined as an incidence of post-thrombotic syndrome <20%.

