### 3.5 Continuation of anticoagulation criteria

Participants will be continued on anticoagulation longer than one month after catheter removal if any of the following criteria exist:

1. Development of thrombosis other than the CRT
2. Extension of the catheter-related thrombosis (i.e. additional vein occlusion on imaging obtained for clinical reasons)

If an enrolled subject at MCW requires anticoagulation longer than 1 month after catheter removal, laboratory assessments will not be completed as the testing can be affected by the presence of an anticoagulant. The participant will not be removed from the study and will be followed for PTS outcomes.

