#### **10.4 Stopping Rules**

The DSMC can consider stopping the study prior to completion if:

1. The intervention is associated with adverse events that call into question the safety of the intervention
  - a. Interim analysis after 20 patients shows an incidence of thrombotic recurrence >40% (8/20 patients)
    - i. Rationale: A retrospective review of CRT in patients with hematologic malignancy at MCW found development of thrombosis other than CRT or extension of the catheter-related thrombosis in 20/141 (14%) of patients. Recurrent thrombosis has been reported in other studies in 20% of cancer patients. If after half of patients are recruited, the thrombotic incidence has doubled over the reported incidence in the literature, the study will be stopped. This level was chosen because it would be unlikely that if 8 events in the first 20 patients occur that no thrombotic events would occur in the next 20 patients to have an overall 20% (8/40) recurrent thrombosis incidence.

2. Difficulty in study recruitment or retention will significantly impact the ability to evaluate the study endpoints
3. New information becomes available that necessitates stopping the trial

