#### **11.1.3: Secondary Endpoints**

1. Recurrent thrombosis
2. Incidence of major and clinically relevant non-major bleeding
3. Reliability of QuickDASH questionnaire in patients with catheter-related thrombosis

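### The planned recurrence analyses do not separate events on anticoagulation from events after stopping, so they estimate the whole strategy and not the risk after stopping at 1 month

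*Combined protocol and SAP*

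**What the plan says.** Objective 3 in section 2.2 is "To determine the incidence of post-thrombotic syndrome, thrombotic recurrence and bleeding in cancer patients with catheter-related thrombosis treated with 1 month of anticoagulation". Section 1 says that the pilot's "estimates will allow an appropriate comparison of duration of anticoagulation to be selected for a future randomized trial", and that its data will supply sample size estimates for a larger study.

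Section 11.1.3 names the endpoint only as "Recurrent thrombosis", with no definition, time origin or at-risk window. Section 11.2 plans three summaries:
- Simple proportions: "The incidence of PTS, thrombotic recurrence, major bleeding and clinically relevant non-major bleeding will be reported as proportions".
- A contingency-table comparison of the same outcomes at months 3 and 6.
- A time-to-event analysis, of which the plan says only this: "A Cox-proportional hazards model will be utilized to calculate the risk of PTS and thrombosis recurrence".

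Sections 4.1 and 5.1 aim for enrolment before catheter removal and require it before anticoagulation ends. Visits 3 and 4 are timed from catheter removal. Section 3.5 says "Participants will be continued on anticoagulation longer than one month after catheter removal if any of the following criteria exist". Its two criteria are a thrombosis separate from the catheter-related one and extension of the catheter-related one. Such patients stay in the study for PTS follow-up.

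The rationale for the interim rule in section 10.4 cites a retrospective review that found "development of thrombosis other than CRT or extension of the catheter-related thrombosis in 20/141 (14%) of patients". These are the same two kinds of event that trigger continuation under 3.5.

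**The concern.** Observation starts on drug and runs past the stop. A patient whose event comes before the planned stop continues treatment under 3.5 and so never experiences stopping at 1 month. Nothing in 11.1.3 or 11.2 keeps that event out of the recurrence rate or that patient out of its denominator. The rate would then describe what happens under the protocol's policy from enrolment onward, while objective 3 and the stated use in section 1 invite the reader to take it as the result of a 1-month course.

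For a duration question the difference matters. Table 1 puts typical care at 1 to 3 months after catheter removal. Any two durations of at least 1 month share the same treatment up to month 1, so events before that point cannot be changed by the choice between them. A rate that mixes the two kinds of event can lead a planner to assume that all of it responds to duration. It also gives the DSMC a total with no indication of how much followed stopping.

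**Working it through.** **Inputs from the documents.** 50 completers and 56 enrolled (4.3); 20/141 and the 8/20 interim figure (10.4); 20% recurrence in other studies (10.4).

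**The plan's own figures.** 50/(1 − 0.10) = 55.6, rounded up to 56. 20/141 = 14.2%. 8/20 = 40%. All reproduce, and none depends on the on-drug/off-drug split.

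**Do the other planned analyses make the split?** The 3- and 6-month comparisons run from catheter removal, so each window contains the planned on-drug month. The Cox model has no stated origin, censoring rule or term for anticoagulation status. Neither isolates post-stop events.

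**Post-stop risk.** Let N be the patients followed, E all recurrences, and k those before the stop. The overall rate is E/N; the post-stop risk is (E − k)/(N − k). The documents do not give k, so it is an assumption. I also assume N = 50, at most one event per patient, and that every event-free patient stops at 1 month. The 14% rate gives E = 7. Intervals are exact (Clopper-Pearson).

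| k before stop (assumed) | Overall | Post-stop risk | Exact 95% CI |
|---|---|---|---|
| 0 | 7/50 = 14.0% | 7/50 = 14.0% | 5.8–26.7% |
| 2 | 7/50 = 14.0% | 5/48 = 10.4% | 3.5–22.7% |
| 4 | 7/50 = 14.0% | 3/46 = 6.5% | 1.4–17.9% |
| 5 | 7/50 = 14.0% | 2/45 = 4.4% | 0.5–15.1% |
| 7 | 7/50 = 14.0% | 0/43 = 0% | 0–8.2% |

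With the 20% rate (10/50), the post-stop risk runs from 10/50 = 20% at k = 0 through 5/45 = 11.1% at k = 5 to 0/40 = 0% at k = 10.

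**Interim look.** With 8 events in 20 patients, k = 0, 4 or 8 gives a post-stop risk of 8/20 = 40%, 4/16 = 25% or 0/12 = 0%. The reported total is 40% in each case.

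**Consequence for a later trial.** Illustration with k = 2, a halving of the events that duration can affect, two-sided 5% and 80% power: n per arm = 7.849 × (p1q1 + p2q2)/(p1 − p2)², with q = 1 − p.
- Whole 14% assumed to respond (14% v 7%): 7.849 × (0.1204 + 0.0651)/0.0049 ≈ 297.
- Randomised at the stop decision (10.4% v 5.2%): 7.849 × (0.0933 + 0.0494)/0.00271 ≈ 413.
- Randomised earlier, only the post-stop part halved: 2/50 = 4% is fixed and 5/50 = 10% falls to 5%, so 14% v 9%: 7.849 × (0.1204 + 0.0819)/0.0025 ≈ 635.

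The answer depends on both the split and the point of randomisation.

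**The case against.** **The whole-strategy rate is a legitimate target.** The protocol's policy is 1 month after removal with the 3.5 rule, and continuing patients are kept in the study. A descriptive pilot may report incidence under that policy. This stands, so the overall rate should stay. A reader might infer that it is wrong or necessarily inflated; the documents do not support that, because the split is unknown and the two rates coincide when k = 0.

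**Mixing is inferred.** 11.1.3 does not define recurrence, and the 20/141 figure describes a historical cohort. That is fair, but nothing excludes on-drug events and 10.4 uses the 3.5 events as its benchmark. An undefined endpoint calls for the same repair.

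**The post-stop rate is not automatically the one to size on.** It conditions on being event-free and stopping on time. It suits a trial that randomises at the stop decision; section 1 leaves that design open. This also stands.

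**The on-drug window may be short.** Section 5.2 allows up to 7 months of anticoagulation, but some of that can precede enrolment, which may follow removal by up to a month (3.3). On the removal-based clock, planned on-drug time is about 1 of 6 months. This limits the likely size of k but does not fix it.

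**The biomarker regression.** A reader might infer that it shares the problem. It does not in effect: 3.5 leaves MCW patients who continue beyond 1 month without laboratory assessments, so they have no predictor value and fall out of the model.

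**Precision.** In the table, the post-stop intervals for k = 2, 4 and 5 all include 14%. The pilot can describe the split but cannot estimate either part tightly.

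**Conclusion.** The point holds. The analyses in 11.2 give recurrence under the whole strategy, and none gives the recurrence risk after stopping at 1 month. The difference cannot be sized from the documents: on assumed splits of 0, 2, 4 or 5 on-drug events out of 7 in 50, the post-stop risk is 14.0%, 10.4%, 6.5% or 4.4%, and the gap is zero if all events follow the stop. These figures rest on N = 50, the 14% rate from the retrospective review, and all event-free patients stopping on schedule.

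This is a secondary endpoint of a feasibility pilot and the feasibility targets are unaffected. The change is still worth making beforehand, because the estimates are meant to inform a duration trial and a split specified in advance avoids attributing events after the data are seen.

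**What to change.** In 11.1.3 and 11.2:
1. Define recurrent thrombosis, including whether extension counts, and state the time origin.
2. Keep overall recurrence, labelled as the whole-strategy estimate.
3. Add (a) recurrence or extension from enrolment to each patient's actual anticoagulant stop date, and (b) recurrence from that date to 6 months after catheter removal among event-free patients who stopped at 1 month, with an exact 95% CI.
4. Record the stop date explicitly. Section 8.2 lists the recurrence date but not this one. Medications are documented at every visit (Table 2), patients are telephoned before stopping, and Visit 2 is timed from the stop, so it should be obtainable.
5. Show (a) and (b) beside the total in the interim DSMC report, leaving the threshold in 10.4 on total events.
6. State that planning of the later trial will use the rate matching its randomisation point: (b) if patients are randomised at the stop decision; otherwise the overall rate with only the post-stop part assumed to respond to duration.

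The cost is a short text change, one data field and two table rows, with no change to treatment, visits or samples. The downside is a wide interval on each part, for example 3.5–22.7% for 5/48, so both should be reported as descriptive.

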## 4. Study Design

### 4.1 Study Overview

[figure not shown]

Figure 1 shows the overall study design of the multicenter prospective cohort of cancer patients with catheter-related thrombosis. Participants may be referred for screening at MCW in two possible mechanisms: participant contact study staff from information on CTSI FACT website or referral from treating Hematologist or Oncologist. At MCW, an EPIC report will be generated to identify people with CRT. The treating provider would then be contacted to determine if referral to the study was appropriate. Subjects at OSU will be referred from the treating Hematologist or Oncologist. A report generated in Epic will be used to identify people with CRT. The treating provider would then be contacted to determine if referral to the study was appropriate. Participants will be given printed information about the study (Appendix A) or verbal explanation using the informational flyer. Verbal consent will be obtained to be screened for participation and contacted by study personnel. Screening will be completed by BCW nurse coordinator (Script Appendix B; Screening form Appendix C). We aim to consent and enroll patients after diagnosis of catheter-related thrombosis and prior to catheter removal. Consent and enrollment (Visit 1) must occur prior to discontinuation of anticoagulation. Enrollment will be limited to patients undergoing anticoagulation with either enoxaparin or a direct oral anticoagulant at the discretion of the treating provider. The study will follow patients treated with anticoagulation for one month after catheter removal. Prior to discontinuation of anticoagulation, patients will be contacted via telephone to review study protocol, assess for bleeding, and arrange for Visit 2 in the following 1-2 weeks. Appendices D-H include the background information that will be collected. Visits 3 and 4 will occur 3 and 6 months after catheter removal, respectively. At visits 3 & 4, Medical history, cancer history, and medications will be updated (Appendices E-G). At each visit, participants will be assessed for post-thrombotic

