### **5.2 Anticoagulation**

Participants will be treated with either enoxaparin for one month following catheter removal, or direct oral anticoagulant treatment (apixaban, rivaroxaban, dabigatran, or edoxaban). Dosing an alternate enoxaparin dose or interval based on anti-factor Xa testing that was obtained by clinical team, at standard dosing per FDA package insert. Anticoagulation will be continued for 1 month after catheter removal. The minimum duration of anticoagulation will be one month and maximum duration is 7 months. The cost of enoxaparin or direct oral anticoagulant treatment will be the responsibility of the participant as use of the medication is part of routine care. Subjects will be contacted by telephone prior to discontinuation of anticoagulation to review if any continuation rules apply and arrange for research visit 2.

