### **5.4 Catheter removal**

The timing and mechanism of catheter or port removal will be directed by the subjects' treating physician. The practitioner type (ex. MD Interventional Radiologist vs RN PICC

Team) will be recorded. Additionally, the reason for catheter removal will be recorded. In a patient that requires catheter or port re-insertion while on enoxaparin or direct oral coagulant therapy, the enoxaparin or direct oral coagulant therapy will be continued for 30 days following removal of all catheters or ports provided the time of anticoagulation does not exceed 6 months duration. If a patient requires re-insertion of a catheter or port after discontinuation of enoxaparin or direct oral anticoagulant therapy, they will be removed from the study at that time because a new catheter would be an additional thrombotic inciting factor.

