## 9. Adverse Event Monitoring

### 9.1 Definitions

**Adverse Event (AE)** – Any untoward or unfavorable medical occurrence in a human subject related to bleeding or thrombosis, including any abnormal sign (for example, abnormal physical exam or laboratory finding), symptom, or disease, temporally associated with the subject's participation in research, whether or not considered related to the subject's participation in research.

**Serious Adverse Event (SAE)** – Any adverse event temporally associated with the subject's participation in research and related to bleeding or thrombosis that meets any of the following criteria:

- Results in death;
- Is life-threatening (places subject at immediate risk of death from the event as it occurs);
- Requires inpatient hospitalization or prolongation of existing hospitalization;
- Results in a persistent significant/incapacity;
- Results in a congenital anomaly/birth defect; or
- Any other adverse event that, based upon appropriate medical judgment, may jeopardize the subject's health and may require medical or surgical intervention to prevent on the other outcomes listed in this definition

Note that seriousness and severity are separate concepts. The term "severe" refers to the intensity of a specific event; a severe event may be of minor medical significance (e.g., a severe leg cramp). The term "serious" is based on an outcome or action criteria that are usually associated with events that pose a threat to the patient's life or functioning. An event that is mild in severity is serious if it leads to one of the outcomes defined above.

Grade 4 and 5 events will always be considered Serious Adverse Events. Many Grade 3 and some Grade 1 and 2 events may meet the definition of a Serious Adverse Event.

Unexpected Adverse Event- Any adverse event occurring in one or more subjects in a research protocol, the nature, the severity, or frequency of which is not consistent with either:

- The known or foreseeable risk of adverse events associated with the procedures involved in the research that are described in;
  - the protocol related documents or the current IRB-approved informed consent document and;
  - other relevant sources of information, such as a product labeling or package insert or;
- The expected natural progression of any underlying disease, disorder, or condition of the subject(s) experiencing the adverse event and the subject's predisposing risk factor profile for the adverse event.

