**Less Likely:**

**Blood Sampling:** Venipuncture can cause, bruising, fainting or local infection at the needle site.

**Survey:** Filling out the surveys could cause stress or anxiety to the participant

**Physical Exam:** Examining the chest cause participant embarrassment

**Anticoagulation:** Use of anticoagulation is known to cause an increased risk of bleeding that can occur at the injection site or systemically. Use of anticoagulation is known to cause an increased risk of bleeding that can occur at the injection site or systemically. Participants will have had anticoagulation for 0-6 months prior to catheter removal and one month after catheter removal. Usual care would include anticoagulation between 1-3 months after catheter removal. With a shortened course of anticoagulation, an increased risk of thrombosis or post-thrombotic syndrome could occur.

Potential side effects of enoxaparin include fever, nausea, diarrhea, fluid retention, elevated LFTs, decreased platelets, decreased RBCs, local irritation, hematoma and redness.

A potential side effect of all direct oral anticoagulant treatment includes bleeding. Edoxaban also reported a rash, abnormal liver function tests, and anemia. Dabigatran is also associated with gastritis-like symptoms in 15% of patients.

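### The 3- versus 6-month Chi-square/Fisher comparison in section 11.2 treats the same patients as two independent groups, and for cumulative outcomes it tests nothing meaningful

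*Combined protocol and SAP*

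**What the plan says.** Section 11.2 (Statistical Analysis) contains three relevant sentences.

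- Summary measure: "The incidence of PTS, thrombotic recurrence, major bleeding and clinically relevant non-major bleeding will be reported as proportions".
- Test: "These outcomes will be compared at 3 and 6 months using Chi-square or Fisher's exact tests".
- Time-to-event model: "A Cox-proportional hazards model will be utilized to calculate the risk of PTS and thrombosis recurrence". Bleeding is not in it.

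Clot presentation and location are dealt with in a separate sentence, also with Chi-square or Fisher's exact tests, as predictors of PTS and recurrence. No paired or repeated-measures method is named for comparing the two time points.

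Section 1 describes a prospective cohort with one treatment duration. Section 5.5 places Visits 3 and 4 at 3 and 6 months after catheter removal and repeats the PTS assessment at each. Section 11.1.2 sets the clinical endpoint as PTS incidence below 20% at 6 months. Section 11.1.3 lists recurrence and bleeding as secondary endpoints. The significance level is 0.05.

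**The concern.** A Chi-square or Fisher table with 3 months in one row and 6 months in the other enters each patient twice. With 50 completers it is analysed as if there were 100 people. The consequence depends on how the outcome is counted, which section 11.2 does not state.

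- **Cumulative outcomes (bleeding, recurrence).** Everyone with an event by 3 months also has one by 6 months. The null hypothesis of equal risk then says that no new event can occur in months 3 to 6, and a single new event refutes it. A large p-value could be misread as showing no further bleeding or recurrence after month 3.
- **PTS as status at each visit.** A patient can gain or lose PTS, so a comparison is sensible, but the two readings are correlated. Ignoring that overstates the variance of the change and can hide a real one.

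The pilot's estimates are meant to inform a future randomised trial of anticoagulation duration (section 1), so a misleading p-value on change over time could be carried forward.

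**Working it through.** **Inputs.** Completers: 50 (section 4.3). Level: 0.05 (section 11.2), taken as two-sided, which the plan does not say. The plan gives no figure for this test and no bleeding rate. Event counts, correlations and hazards below are assumptions for illustration.

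**The plan's own figures (section 4.3).** Exact (Clopper-Pearson) 95% intervals: 40/50 gives 66.3-90.0% (plan 66-90%); 45/50 gives 78.2-96.7% (plan 78-96%). For 5/50 the one-sided 95% upper bound is 19.9% (plan: not above 20%). 50/0.9 = 55.6, so 56 enrolled. These reproduce apart from rounding, and none involves the 3- versus 6-month test.

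**Step 1: nested counts.** Let a patients have the event by 3 months and b by 6 months, the first set contained in the second. Uncorrected Chi-square is z = (b − a)/50 ÷ √[p(1 − p)(2/50)], with p = (a + b)/100. When all b − a changes go one way, exact McNemar is p = 2 × 0.5^(b − a).

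- 5 then 10: z = 0.10/√(0.15 × 0.85 × 0.04) = 1.40. McNemar is 2 × 0.5^5 = 0.0625.
- 2 then 8: z = 0.12/√(0.10 × 0.90 × 0.04) = 2.00. McNemar is 2 × 0.5^6 = 0.031.
- 4 then 12: z = 0.16/√(0.16 × 0.84 × 0.04) = 2.18. McNemar is 2 × 0.5^8 = 0.008.

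| 3 months, then 6 months (of 50) | Fisher p | Chi-square p | Exact McNemar p |
|---|---|---|---|
| 5, then 10 | 0.26 | 0.16 | 0.063 |
| 2, then 8 | 0.092 | 0.046 | 0.031 |
| 4, then 12 | 0.054 | 0.029 | 0.008 |

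McNemar is shown to measure the effect of ignoring the pairing. For a cumulative outcome it has no useful null hypothesis either.

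**Step 2: what it takes to reach p < 0.05 from 2/50.** Fisher needs 10/50 (p = 0.028), that is 8 new events in months 3 to 6. Uncorrected Chi-square needs 8/50 (p = 0.046), that is 6. A change from 2/50 to 3/50 gives Fisher p = 1.00.

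**Step 3: PTS as visit status.** With equal true prevalence p at both visits and within-patient correlation r, the difference has variance 2p(1 − p)(1 − r)/50. The unpaired test uses 2p(1 − p)/50, which is too large when r > 0. Simulation (n = 50, 40,000 runs, prevalence 10% or 20%) puts the real size of the nominal 5% Chi-square test at about 2.1% for r = 0.3, 0.7-0.8% for r = 0.5 and 0.1% for r = 0.7. For a true change from 10% to 25% with r = 0.5, power is about 36% with Fisher and 70% with exact McNemar.

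**Step 4: could an on-/off-drug split of bleeding be informative?** Assume one month on drug and five off, with monthly hazards on/off of 1%/0.9%, 3%/0.5% or 5%/0.1%. The exponents are 0.01 + 5 × 0.009 = 0.03 + 5 × 0.005 = 0.05 + 5 × 0.001 = 0.055. All three therefore give a 6-month risk of 1 − exp(−0.055) = 5.4%, or 2.7 bleeds in 50. Now suppose 2 bleeds in 50 on-drug patient-months: 4.0 per 100, exact Poisson 95% interval 0.5-14.4. Suppose 1 bleed in 250 off-drug patient-months: 0.4 per 100, interval 0.01-2.2. These intervals cover every assumed on-drug rate (1, 3, 5) and every assumed off-drug rate (0.9, 0.5, 0.1).

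**The case against.** **The wording is loose.** Section 11.2 does not say outright that 3 months is tested against 6 months; it could mean a comparison between groups at each time. This stands in part. But no groups are named in that sentence, the study has one cohort, and the clot-characteristic comparisons have their own sentence. If groups were meant, they need naming, so the sentence needs correcting either way.

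**Nothing depends on the p-value, and the error is usually conservative.** This stands. Success is PTS below 20% (sections 2.2 and 11.1.2), and the stopping rule uses the recurrence count (section 10.4). A reader might infer an excess of false positives; Step 3 points the other way.

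**A stronger reading is tempting: that the bleeding proportions are themselves wrong because they mix time on and off drug with unequal exposure.** Total drug time does vary: "The minimum duration of anticoagulation will be one month and maximum duration is 7 months", and "Participants will have had anticoagulation for 0-6 months prior to catheter removal and one month after catheter removal". Enrolment can be late, since "Consent and enrollment (Visit 1) must occur prior to discontinuation of anticoagulation", and a patient given a new catheter after stopping leaves: "they will be removed from the study at that time because a new catheter would be an additional thrombotic inciting factor". The documents still do not make this an error:

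- Objective 3 (section 2.2) and section 11.1.3 ask for the incidence of bleeding, which a proportion answers. No on-drug rate is asked for.
- Widely unequal observed drug time arises only if bleeds are counted from enrolment. That can be inferred from the adverse-event definition ("temporally associated with the subject's participation in research", section 9.1), but the endpoint does not state it. Counted from removal, drug time is one month by design, apart from the continuation cases in section 3.5 and catheter re-insertion on drug in section 5.4.
- Loss to new catheters is limited by exclusion 4, sits within the planned 10% dropout, and affects every outcome.
- Leaving bleeding out of the Cox model is no defect with about three events, as in the scenarios of Step 4.

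**Conclusion.** The concern holds for the 3- versus 6-month test, and for all the outcomes it covers, not only bleeding. On the natural reading of section 11.2, an independent-samples test is applied to one set of patients. For bleeding and recurrence counted cumulatively, the p-value has no meaning. For PTS as visit status, the test is valid in neither size nor power, and it errs towards missing a change. If bleeds were instead counted separately in months 0-3 and 3-6, the counts would not be nested, but the patients would still be the same.

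The size of the error depends on assumed counts and correlations: at 5 then 10 of 50, p = 0.26 against 0.063 with pairing respected. The threshold from 2/50 depends on the test chosen, so the Fisher figure of 10/50 should not be quoted for both.

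Severity is minor. The sample size, success criterion and stopping rule are unaffected. The documents do not support going further and calling the bleeding proportions invalid.

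**What to change.** In section 11.2:

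1. Drop the 3- versus 6-month test for bleeding and recurrence. Report cumulative proportions at 3 and 6 months with exact 95% confidence intervals and stated denominators. For example, 2/50 is 4.0% (0.5-13.7%) and 3/50 is 6.0% (1.3-16.5%).
2. State whether PTS is compared as status at each visit. If so, use McNemar's exact test in patients assessed at both visits, or report the paired change with a confidence interval.
3. If a between-group comparison at each visit was intended, name the groups.

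Optional, descriptive only, and not a correction: list how many first bleeds fell on drug and after stopping, with patient-months of each. Section 8.2 records bleed dates and the Table 2 schedule documents medications at Visits 1-4. The data-collection appendices are not available here, so check that a last-dose date is captured. Events will be too few to separate the rates.

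The cost is a few lines of text, with no new visits and no change in enrolment. The optional listing adds one small table and at most one data field.
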